10 DATA MANAGEMENT AND QUALITY ASSURANCE

The Investigator will maintain accurate source documentation including patient medical records, laboratory reports, ECG strips, and patient diaries.

Investigative site qualified personnel will enter patient data into an EDC system. The analysis data sets will be a combination of these data and data from other sources.

Clinical data management will be performed in accordance with applicable standards and data cleaning procedures to ensure the integrity of the data (e.g., removing errors and inconsistencies in the data). Adverse events will be coded using the Medical Dictionary for Regulatory Activities (MedDRA). Concomitant medications will be coded using the world health organization (WHO) Drug Dictionary.

After database lock, each study site will receive information about all of their site-specific eCRF data as entered into the EDC system for the study, including full discrepancy and audit history. Additionally, a copy of study data from all sites will be created and sent to the Sponsor for storage. The CRO will maintain a duplicate copy for its records. In all cases, patient initials will not be collected or transmitted to the Sponsor.

For detailed instruction on data entry procedures and timelines, please refer to the eCRF Completion Guidelines.

11 ETHICAL, REGULATORY, AND STUDY MANAGEMENT CONSIDERATIONS

11.1 Regulatory and Ethical Conduct of the Study

The study will be performed in accordance with the ethical principles that have their origin in the Declaration of Helsinki, International Council for Harmonisation (ICH) Good Clinical Practice (GCP), and all applicable regulations.

11.2 Independent Ethics Committee or Institutional Review Board

Federal regulations and ICH guidelines require that approval be obtained from an institutional review board (IRB)/IEC before participation of human patients in research studies. Before study onset, the protocol, informed consent, advertisements to be used for the recruitment of study patients, and any other written information regarding this study intended to be provided to the patient or the patient's legally authorized representative must be approved by the IRB/IEC. Documentation of all IRB/IEC approvals will be maintained by the site and will be available for review by the Sponsor or its designee.

All IRB/IEC approvals should be signed by the IRB/IEC chairman or designee and must identify the IRB/IEC name and address, the clinical protocol by title or protocol number or both, and the date approval or a favorable opinion was granted.

The Investigator is responsible for obtaining continued review of the clinical research as specified by the IRB/IEC, at intervals not exceeding 1 year. The Investigator must supply the Sponsor or its designee with written documentation of continued review of the clinical research.

11.3 Patient Information and Consent

Informed consent in compliance with IRB/IEC and local regulations shall be obtained from each patient or their legally authorized representative before performing any study procedures and will be documented with a signed IRB/IEC approved ICF. Before enrollment, each prospective patient or his or her legally authorized representative will be given a full explanation of the study and be allowed to read the approved ICF. Once the Investigator is assured that the patient/legally authorized representative understands the implications of participating in the study, the patient/legally authorized representative will be asked to give consent to participate in the study and sign the ICF. The process for obtaining consent has to be documented at the institution.

If the ICF is revised during the course of the study, all patients on-study, including those in follow-up, must sign the revised form, unless otherwise indicated by the IRB/IEC (local or global, as applicable). In such cases, the reason for not re-consenting the patient should be documented.

11.4 Confidentiality

All laboratory specimens, evaluation forms, reports, and other records will be identified in a manner designed to maintain patient confidentiality. All records will be kept in a secure storage area with limited access. Clinical information will not be released without the written permission of the patient (or the patient's legal guardian), except as necessary for monitoring and auditing by the Sponsor, its designee, regulatory authorities, or the IRB/IEC.

The Investigator and other study staff may not disclose or use for any purpose other than performance of the study any data, record, or other unpublished, confidential information disclosed to those individuals for the purpose of the study. Prior written agreement from the Sponsor or its designee must be obtained for the disclosure of any said confidential information to other parties.

11.5 Financial Disclosure and Obligations

Investigators are required to provide financial disclosure information to allow the Sponsor to submit the complete and accurate certification or disclosure statements as required under 21 CFR 54 and local regulations. In addition, the Investigator must promptly update this information if any relevant changes occur during the course of the investigation and for 1 year following the completion of the study.

11.6 Study Conduct

The Investigator will conduct all aspects of this study in accordance with the principles of the current version of ICH E6 as well as all national, state, and local laws and regulations. Study personnel involved in conducting this study will be qualified by education training and experience to perform their respective tasks. Study information from this protocol will be posted on publicly available clinical study registers before enrollment of patients begins.

11.7 Protocol Amendments

Any change in the study plan requires a protocol amendment. All amendments to the protocol must be reviewed and approved following the same process as the original protocol before the amended protocol can be implemented. The Investigator will inform the governing IRB/IEC of all protocol amendments issued by the Sponsor in accordance with established IRB/IEC procedure. Only protocol amendments intended to eliminate an apparent immediate hazard to patient(s) may be implemented immediately, i.e., without IRB/IEC approval, but the circumstances of the change must be documented and submitted to the IRB/IEC.

11.8 Monitoring of the Study

All aspects of the study will be carefully monitored by the Sponsor or designee for compliance with GCP and applicable government regulations.

Investigators and institutions involved in the study will permit study-related monitoring, audits, IRB/IEC review, and regulatory inspections by providing direct access to all study records. In the event of an audit, the Investigator agrees to allow the Sponsor, representatives of the Sponsor, or a regulatory agency access to all study records.

The Investigator should promptly notify the Sponsor and the CRO of any inspections scheduled by any regulatory authorities and promptly forward copies of any inspection reports received to the Sponsor.

11.9 Records Retention

Essential documents should be retained for at least 15 years from the completion of the study (last patient last visit) or until at least 2 years after the last approval of a marketing application in an ICH region or until there are no pending or contemplated marketing applications in an ICH region or at least 2 years have elapsed since the formal discontinuation of clinical development of the investigational study drug. However, these documents should be retained

for a longer period if required by the applicable regulatory requirements or by an agreement with the Sponsor. It is the responsibility of the Sponsor to inform the Investigator/institution as to when these documents no longer need to be retained.

11.10 Publications

Following completion of the study, the results from the study may be reported publicly by making any oral public presentation and/or submitting or presenting a manuscript, abstract, or other materials relating to the Study at scientific meetings and/or to a publisher, reviewer, or other outside person in scientific journals (“Publication”), provided, however, that Publication of the results from an individual site shall not be made before the first multi-site Publication by Sponsor. The Sponsor shall coordinate the drafting, editing, authorship, and other activities related to study Publication and shall mutually agree with the Investigator(s) on the number, medium, forum, and timing for Publication. The Sponsor shall solicit input regarding contents of the Publication from all Investigators and in consultation with all sites. The Sponsor acknowledges the right of the Investigator(s) to publish the results of this study after the entire study has completed, but also reserves the right to a window to review the Publication for regulatory compliance as well as for protection of its intellectual property. In particular, the Sponsor may request to remove the Sponsor’s confidential information and suspend Publication for a certain period of time to protect the Sponsor’s intellectual property interest, as further set forth in the Clinical Trial Agreement with the clinical study site(s) and Investigator(s).

This SAP should be read in conjunction with the study protocol and case report form (CRF). This version of the plan has been developed using the Protocol Amendment 7 dated 2 September 2021.

[figure not shown]
2 Study Objectives

2.1 Primary Objectives

- Characterize the safety and tolerability of camidanlumab tesirine as monotherapy and camidanlumab tesirine in combination with pembrolizumab, and to identify the recommended dose(s) and schedule(s) for future studies in patients with selected advanced solid tumors

2.2 Secondary Objectives

- Evaluate the preliminary anti-tumor activity of camidanlumab tesirine as monotherapy and camidanlumab tesirine in combination with pembrolizumab
- Evaluate the pharmacokinetic (PK) profile of camidanlumab tesirine as monotherapy and camidanlumab tesirine in combination with pembrolizumab
- Evaluate the immunogenicity of camidanlumab tesirine as monotherapy and camidanlumab tesirine in combination with pembrolizumab

3 Study Design

This is a Phase 1b, multi-center, open-label study with a dose-escalation part and a dose-expansion part.

In the dose-escalation part (Part 1), patients will receive escalating doses of camidanlumab tesirine as monotherapy, or escalating dose of camidanlumab tesirine in combination with pembrolizumab, guided by a 3+3 design.

Additionally, in the dose-escalation part for camidanlumab tesirine as monotherapy, separate paired-biopsy cohorts have been included:

- The paired-biopsy cohorts will enroll patients, treated only with camidanlumab tesirine as monotherapy, who will be undergoing two mandatory biopsies, one pre- and one on-treatment biopsy, to better understand effects of camidanlumab tesirine on tumor tissue biomarkers. These cohorts will be introduced at dose levels that have been deemed safe during escalation. In order to allow patients to benefit from trial participation, one intra-patient dose escalation (after the mandatory on-treatment biopsy has been obtained) to the highest dose level determined to be safe at that point will be performed, unless deemed by the Investigator not to be in the best interest of the patient.

Two groups are planned in the dose-expansion part (Part 2):

- Group 1: an indication for which camidanlumab tesirine in combination with pembrolizumab at the doses shown in Part 1 to have preliminary activity.
- Group 2: a basket group of patients with advanced solid tumors and MSI-H/dMMR status, who have received a prior regimen containing a PD-1/PD-L1 inhibitors, for which the best response was CR, PR, or SD ≥ 4 months, and then progressed while under treatment with the PD-1/PD-L1 inhibitor based regimen; no more than 4 patients with the same indication (tumour type) are allowed in this basket group.

3.1 Sample Size Consideration

Approximately 95 patients; Part 1 may enroll approximately 65 patients and Part 2 will enroll approximately 30 patients, approximately 16 patients in Group 1 and 14 in Group 2.

3.2 Randomization

Not applicable.

3.3 Modifications to the statistical section of the protocol

Not applicable.

4 Statistical methods

No hypothesis testing will be performed in this study.

All analyses will use SAS® version 9.4 or higher.

Unless otherwise stated, tables, listings, and figures will be broken down by monotherapy and combination therapy and then by dose level in dose-escalation part, and by group in dose-expansion part. Additional tables broken down by indication and by indication at recommended dose for expansion (RDE) will be specified in later sections. All data will be provided in listings. Tables and figures are based on the defined analysis population.

Categorical data will be presented using counts and percentages, with the number of patients in the analysis population as the denominator for percentages. Percentages will be rounded to 1 decimal place and not be displayed for zero counts.

Continuous data will be summarized using the number of observations (n), mean, standard deviation (std), median, minimum, and maximum. Minima and maxima will be rounded to the precision of the original value, and means, medians, and 95% confidence intervals (CIs) if presented will be rounded to 1 decimal place greater than the precision of the original value. The std will be rounded to 2 decimal places greater than the precision of the original value, up to a maximum of 3 decimal places.

CI will be two-sided and use $\alpha=0.05$ (i.e., 95% CIs), unless otherwise specified. For exact estimates, the CI will be calculated using the Clopper–Pearson exact method. For Kaplan–Meier estimates, the CI will be calculated using the Greenwood's formula with (complementary) log-log transformation.

Kaplan–Meier plots will be provided along with Kaplan–Meier estimates.

The Baseline value is defined as the last non-missing value or measurement taken prior to the first dose of study drug.

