- Changes from Baseline of safety laboratory values, vital signs, Eastern Cooperative Oncology Group (ECOG) performance status, and 12-lead electrocardiograms (ECGs) for patients treated with camidanlumab tesirine as monotherapy and for patients treated with camidanlumab tesirine in combination with pembrolizumab
- Frequency of dose interruptions and dose reductions for patients treated with camidanlumab tesirine as monotherapy and for patients treated with camidanlumab tesirine in combination with pembrolizumab
- Incidence of dose limiting toxicities (DLTs) (dose-escalation only) for patients treated with camidanlumab tesirine as monotherapy and for patients treated with camidanlumab tesirine in combination with pembrolizumab

Secondary Endpoints

- Overall response rate (ORR) according to Response Evaluation Criteria In Solid Tumors (RECIST) v1.1, for patients treated with camidanlumab tesirine as monotherapy and for patients treated with camidanlumab tesirine in combination with pembrolizumab
- Duration of response (DOR) defined as the time from the first documentation of tumor response to disease progression, as per RECIST v1.1, or death for patients treated with camidanlumab tesirine as monotherapy and for patients treated with camidanlumab tesirine in combination with pembrolizumab
- Progression-free survival (PFS) defined as the time between start of treatment and the first documentation of recurrence, progression, as per RECIST v1.1, or death for patients treated with camidanlumab tesirine as monotherapy and for patients treated with camidanlumab tesirine in combination with pembrolizumab

- Overall survival (OS) defined as the time between the start of treatment and death from any cause for patients treated with camidanlumab tesirine as monotherapy and for patients treated with camidanlumab tesirine in combination with pembrolizumab
- Concentrations and PK parameters of camidanlumab tesirine total antibody, PBD-conjugated antibody, and unconjugated warhead SG3199 in serum
- Frequency of confirmed positive anti-drug antibody (ADA) responses, their associated titers and, if applicable, neutralizing activity to camidanlumab tesirine after treatment with camidanlumab tesirine

Study Design:

This is a Phase 1b, multi-center, open-label study with a dose-escalation part and a dose-expansion part.

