1.3.4 ADCT-301-103

As of 14 April 2021, enrolment in the monotherapy part was completed; 44 patients were treated with camidanlumab tesirine monotherapy in Part 1 at 8 dose levels ranging from 20 to 150 $\mu\text{g}/\text{kg}$ administered on a 3-week treatment cycle and the MTD has not been reached.

The most frequently reported TEAEs ($\geq 20\%$ overall), regardless of grade or relationship, included: nausea (40.9%), fatigue and decreased appetite (36.4% each), constipation (29.5%), abdominal pain (27.3%), rash (22.7%). ([Puzanov, 2021](#)).

The TEAEs that have been assessed as Grade ≥ 3 were reported in 31 out of 44 (70.5%) patients. The most common Grade ≥ 3 TEAEs (observed in at least 5% of patients overall), regardless of relationship, included anemia (11.4%), abdominal pain, rash and pulmonary embolism (6.8% each).

Grade 3 autoimmune AE (colitis, immune-mediated adverse event, systemic inflammatory response syndrome) and grade 3 neurologic AE (dysphagia and asthenia), regardless of relationship, were observed in 6.8% and 4.5% of the patients, respectively.

Best overall responses were stable disease (SD) for 11 patients (25%) and progressive disease (PD) for 23 patients (52.3%); 2 patients were not evaluable (4.4%) and 8 (18.2%) had no post-baseline evaluation due to death (11.4%) or clinical progression (6.8%).

Some patients with paired biopsies showed decreased Tregs and increased Teffs:Tregs ratio in the local tumor environment, supporting a therapeutic rationale for the treatment of advanced solid tumors with camidanlumab tesirine in combination with other immune-modulating therapies ([Puzanov, 2020](#)).

At the time of this Protocol Amendment 7, the study is enrolling patients receiving camidanlumab tesirine in combination with pembrolizumab.

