4.9 Safety Analyses

All safety analyses will be based on the Safety Analysis Set.

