4.9.2 Laboratory Data

Laboratory data for hematology, chemistry, and coagulation will be summarized for the actual values and the change from baseline value at each scheduled assessment. In addition, all data will be graded according to the NCI CTCAE Version 4.0, and summarized by baseline and maximum post-baseline CTCAE grade, including unscheduled visits. Shift tables will summarize the shift from baseline grade to maximum post-baseline CTCAE grade.

Listings of laboratory data for hematology, chemistry, and coagulation will be provided. In addition, listings of urinalysis, thyroid function testing, influenza testing, SARS-CoV-2 testing, and any microbiological tests performed will also be provided.

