4.9.3 Electrocardiogram

Electrocardiogram (ECG) data will be summarized for the actual values and the change from baseline value at each scheduled assessment. Shift tables will summarize the shift from baseline to End of Treatment and worst post-baseline visit in ECG interpretation (categorized as normal; abnormal, not clinically significant; and abnormal, clinically significant).

Corrected QT interval by Fredericia (QTcF) will be summarized by categories as follows:

- QTcF interval > 450 ms
- QTcF interval > 480 ms
- QTcF interval > 500 ms
- QTcF interval increases from baseline > 30 ms
- QTcF interval increases from baseline > 60 ms

Listings of ECG data will be provided from both local and central reads of the data.

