4.9.5 ECOG Performance Status

ECOG performance status will be summarized at each scheduled assessment. Shift tables will summarize the shift from baseline to End of Treatment and to the worst post-baseline visit in ECOG performance status.

Listing of ECOG performance status will be provided.

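### The SAP's single denominator for categorical data deflates ECOG percentages at each visit as patients leave; shift tables are affected much less and not progressively

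*SAP*

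**What the plan says.** SAP section 4 states the rule for categorical tables: "Categorical data will be presented using counts and percentages, with the number of patients in the analysis population as the denominator for percentages". The sentence carries no exception, although the rules in the same section for table breakdown and for confidence intervals do allow for one. Continuous data are handled differently: "Continuous data will be summarized using the number of observations (n), mean, standard deviation (std), median, minimum, and maximum".

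SAP 4.9 fixes the population: "All safety analyses will be based on the Safety Analysis Set". Under SAP 4.1.1 that means everyone treated. SAP 6.1.1 leaves missing values missing unless something else is specified, and the only missing category it provides is for AE severity.

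The tables concerned are these:

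- **ECOG (SAP 4.9.5):** the by-visit rule is "ECOG performance status will be summarized at each scheduled assessment". This section also asks for shifts to End of Treatment (EOT) and to the worst visit after baseline.
- **Laboratory (SAP 4.9.2):** the by-visit rule is "Laboratory data for hematology, chemistry, and coagulation will be summarized for the actual values and the change from baseline value at each scheduled assessment". Grade shifts are tabulated from baseline to the highest grade seen afterwards.
- **ECG (SAP 4.9.3):** values and changes by visit, and "Shift tables will summarize the shift from baseline to End of Treatment and worst post-baseline visit in ECG interpretation". QTcF threshold categories are listed, without saying whether they are by visit or at any time after baseline.
- **Vital signs (SAP 4.9.4):** values and changes by visit.

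None of these sections names a different denominator. Protocol section 3 places change from baseline in ECOG status, alongside laboratory values, vital signs and ECGs, among the primary endpoints.

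**The concern.** A whole-population denominator suits an incidence: a treated patient either had the event or did not. It does not suit a status at a visit. A patient who has left cannot be counted in any ECOG category, yet still adds one to the denominator. The categories at a late visit then no longer sum to 100%, and the percentage with poor status falls as patients leave, whatever happens to those still assessed.

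Two things are at stake. First, a worsening trend in a primary safety variable can be shown as an improvement. Second, tables are split by dose level, so a level that loses more patients would show lower late ECOG percentages for that reason alone, in a study whose primary objective includes recommending a dose. The SAP is also inconsistent within a visit: mean laboratory change is taken over patients with data, while the percentage at a given ECOG grade is taken over everyone treated.

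**Working it through.** **Plan's own figure.** The plan states none here. The check is of the denominator rule.

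**Formula for by-visit tables.** With x patients in a category, n assessed at the visit and N in the analysis population, the SAP reports x/N and the proportion among assessed patients is x/n. The deflation factor is (x/n) / (x/N) = N/n.

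**Inputs.** N = 44 monotherapy patients (Protocol 1.3.4); N = 16 and 14 for the two expansion groups (Protocol 4.1.2). Retention by visit is not in the documents, so n is assumed over a range.

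| N | n assessed (assumed) | N/n |
|---|---|---|
| 44 | 40 | 1.1 |
| 44 | 33 | 1.33 |
| 44 | 22 | 2.0 |
| 44 | 11 | 4.0 |
| 16 | 8 | 2.0 |
| 16 | 4 | 4.0 |
| 14 | 7 | 2.0 |
| 14 | 4 | 3.5 |

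**Is heavy attrition plausible?** Protocol 1.3.4 gives best responses for the 44: 11 stable disease, 23 progressive disease, 2 not evaluable and 8 with no post-baseline evaluation because of death or clinical progression (11 + 23 + 2 + 8 = 44). Treatment normally ends at progression (Protocol 4.2.2). Substantial attrition is therefore likely, but best response is only a rough proxy for attendance at a visit.

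**Direction of trend, with invented counts.** Suppose 6 of 36 assessed patients have ECOG 2 at an early visit and 3 of 11 at a later one.

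- Among assessed patients: 6/36 = 16.7%, then 3/11 = 27.3%, a rise.
- Under the SAP rule: 6/44 = 13.6%, then 3/44 = 6.8%, a fall.

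**Shift tables.** None is by visit. A patient who leaves after one post-baseline value still counts in the worst-post-baseline shift. The deflation is 1/(1 − m), where m is the share with no post-baseline value:

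- m = 5% (assumed): 1/0.95 = 1.05
- m = 10% (assumed): 1/0.90 = 1.11
- m = 8/44 = 18.2%: 44/36 = 1.22. This assumes that all 8 patients without a tumour evaluation also lacked safety data, which is probably too high.

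For the EOT shift, m is the share with no EOT value. The effect occurs once: 1.11 at 10% and 1/0.70 = 1.43 at 30% (both assumed).

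**Continuous by-visit summaries.** Laboratory, vital-sign and ECG values and changes use the observed n, so the factor is 1.

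**The case against.** A reader might infer that every safety percentage shrinks as patients leave, so that later abnormalities in general look several times rarer than they are. The documents do not support that. No shift table is by visit, laboratory grades and ECG interpretation are not tabulated by visit, and most by-visit safety summaries are continuous. ECOG status is the one safety variable that is clearly both categorical and by visit. Nor is the rule universal across the documents: Protocol 9.10 uses patients tested as the denominator for anti-drug antibodies.

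A reader might also take the 4-fold factor as established by the 11 of 44 with stable disease. It is not. Stable disease needs only 35 days on study (SAP 4.8.1), while Cycle 5 Day 1 is study day 85 (SAP 4.7.1, Table 1), so some of the 11 may not reach it. Conversely, Protocol 7.3 lets clinically stable patients continue until progression is confirmed, so some of the 23 may. The proxy can err either way.

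The practical case against is fair in part. Counts accompany percentages and ECOG data are listed. At 44 patients over 8 dose levels, about 5.5 each, readers will work largely from counts. There is no hypothesis testing, and the escalation and stopping rules use DLTs and AEs. However, the SAP does not require n assessed to be shown in categorical tables, so recovery of the right figure is not assured. The table shells are not among the documents and may already show it.

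The strongest point is that a denominator of assessed patients describes only those still attending. If patients leave because they deteriorate, that percentage can flatter the treatment. This stands as a caution. It is met by displaying n and keeping the worst-post-baseline shift beside the by-visit table.

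**Conclusion.** The point holds for by-visit categorical tables: ECOG status at each scheduled assessment, and the QTcF categories if they are by visit. As written, the SAP deflates these percentages by N/n and can reverse an apparent trend in a primary safety variable. The identity N/n is exact. Its size depends on assumed retention: about 1.1 to 1.3 with 90% to 75% assessed, 2 at 50%, 4 at 25%.

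For shift tables the effect is smaller and does not grow with visit number: about 1.05 to 1.2 for worst-post-baseline shifts, and a single deflation for EOT shifts, again on assumed missingness. Continuous by-visit summaries are sound. The SAP should be corrected, but dose-escalation decisions do not turn on this.

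**What to change.** Add to SAP section 4:

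- For by-visit categorical tables, the denominator is patients with a non-missing value at that visit, and that n is displayed.
- For shift tables, the denominator is patients with a baseline value and the relevant post-baseline value. Alternatively, keep the analysis set and show a missing category.
- For AE incidence, DLT, ORR and DCR, the denominator remains the relevant analysis set.

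In SAP 4.9.3, say whether the QTcF categories are by visit or at any time after baseline, so that it is clear which rule applies.

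The cost is a short addition to the SAP and an n line in the table shells, with no change to data collection. The small downside is that by-visit percentages then describe only patients still assessed, so n must be visible and the worst-post-baseline shift retained.
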